7.4 Dosage Modification

There is no provision for dose modification of study treatment. If a participant interrupts treatment due to an AE, study treatment can be restarted in consultation with the Medical Monitor.

A Pharmacy Manual will not be provided for studies with oral dose formulations.

Dose reductions or dose escalations are not permitted. All dose modification rules apply to all arms given the blinded nature of this study.

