CYP2C8 and CYP3A4 -Strong or moderate inhibitors	clopidogrel, gemfibrozil, clarithromycin, itraconazole	Prohibited during the study	5 PK half-lives or 14 days of randomization
CYP2C8 and CYP3A4 -Strong or moderate inducers	rifampin, phenytoin	Prohibited during the study	3 weeks of the randomization
CYP2C8 or P-gp Sensitive substrates with narrow therapeutic indices	Repaglinide, dabigatran, fexofenadine	Prohibited during the study (digoxin allowed under limited/urgent circumstances; see below)	5 PK half-lives or 14 days of randomization
Immunization against agents other than influenza or SARS-CoV-2	Live vaccines	Prohibited during the study	90 days before and 60 days after EOT
	Nonlive vaccines unassociated with influenza or SARS-CoV-2		30 days before and 60 days after EOT

Table 7.7.1-1: Prohibited and Restricted Medications

Type of Medication	Examples (not exhaustive)	Restriction	Required Washout
Immunization for influenza or SARS-CoV-2	Live vaccines	Prohibited during the study	90 days before and 60 days after EOT
	Nonlive vaccines for influenza or SARS-CoV-2		14 days prior to screening and 60 days after EOT
Immunosuppressants -systemic or oral preparations of herbal immunomodulatory medications	Mycophenolate-mofetil, azathioprine, methotrexate	Prohibited during the study	8 weeks prior to randomization
JAK inhibitors	Tofacitinib, baricitinib, filgotinib, and upadacitinib	Prohibited during the study	8 weeks prior to randomization
Leukotriene inhibitors	montelukast	Prohibited during the study	4 weeks prior to randomization
Monoamine Oxidase Inhibitors	Selegiline, phenelzine	Prohibited during the study	2 weeks prior to randomization
Narcotic analgesics	Oxycodone and, hydrocodone	Prohibited during the study	Not applicable
Non-narcotic analgesics	Acetaminophen	Brief courses for up to 7 days allowed	Not applicable
Phosphodiesterase Inhibitor	Apremilast, crisaborole	Prohibited during the study	3 weeks prior to randomization
Phototherapy	UVB, UVA	Prohibited during the study	4 weeks prior to randomization
S1P Receptor Modulators	Fingolimod, ozanimod, siponimod, etrasimod	Prohibited lifetime use	Not applicable
Treatments to be restricted or suspended during the study	rosiglitazone	Dose up to 4 mg can be used, monitor glucose closely	Not applicable
	torasemide	Dose up to 10 mg can be used	Not applicable

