	digoxin	For acute use only, exclude at baseline; limit highest dose and monitor trough concentrations; stop treatment with IP during treatment with digoxin and for 3 days afterwards	Not applicable
Treatments -Other	Diquafosol, rebamipide	Prohibited during the study	4 weeks prior to randomization

No concomitant medications (prescription, over-the-counter or herbal) are to be administered during study unless they are prescribed for treatment of specific clinical events. Any concomitant therapies must be recorded on the eCRF, along with the reason for its administration.

The investigator should contact and confirm agreement with the BMS medical monitor (and acknowledgement from the contract research organization medical monitor) prior to the administration of any concomitant medications, excepting those needed for urgent/emergent treatment for which there is insufficient time for such contact.

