8 DISCONTINUATION CRITERIA

8.1 Discontinuation from Study Treatment

Participants MUST discontinue investigational product (and non-investigational product at the discretion of the investigator) for any of the following reasons:

- Participant's request to stop study treatment. Participants who request to discontinue study treatment will remain in the study and must continue to be followed for protocol specified follow-up procedures. The only exception to this is when a participant specifically withdraws consent for any further contact with him/her or persons previously authorized by participant to provide this information
- Any clinical adverse event (AE), laboratory abnormality or intercurrent illness which, in the opinion of the investigator, indicates that continued participation in the study is not in the best interest of the participant
- Termination of the study by Bristol-Myers Squibb (BMS)
- Loss of ability to freely provide consent through imprisonment or involuntary incarceration for treatment of either a psychiatric or physical (eg, infectious disease) illness. (Note: Under specific circumstances and only in countries where local regulations permit, a participant who has been imprisoned may be permitted to continue as a participant. Strict conditions apply and BMS approval is required.)
- Asthma or COPD that requires systemic glucocorticoid or biologic treatment, or inhaled budesonide or equivalent at >1200 µg/day or fluticasone propionate at > 880 µg/day along with another anti-asthma/COPD drug such as a long-acting beta-agonist.
- Systemic or photo-based rescue therapy for AD ([Section 7.7.2](#)),
- Replication-competent (live) vaccine
- Grade 4 lymphopenia (ALC < 200) with repeat testing within 7 days (according to the Common Toxicity Criteria for Adverse Events [CTCAE] version 5.0)
- Elevation of ALT or AST > 5x ULN or concurrent elevations of ALT or AST > 3x ULN and bilirubin > 2x ULN
- Decline in PFT values (FEV1 and/or FVC) below 30% of the baseline values
- Diagnosis of macular edema, retinal or choroidal disease or syndrome
- Grade 2 or higher cardiac or bone marrow adverse events (with exception of ALC) according to the CTCAE version 5.0.
- Grade 3 for other system adverse events (according to the CTCAE version 5.0)
- Missed dose of ≥ 3 consecutive days or overall compliance < 85% over a period of > 30 days starting from study Day 1.

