9 STUDY ASSESSMENTS AND PROCEDURES

- Study procedures and timing are summarized in the Schedule of Activities.
- Protocol waivers or exemptions are not allowed.
- All immediate safety concerns must be discussed with the Sponsor immediately upon occurrence or awareness to determine if the participant should continue or discontinue treatment.
- Adherence to the study design requirements, including those specified in the Schedule of Activities, is essential and required for study conduct.
- All screening evaluations must be completed and reviewed to confirm that potential participants meet all eligibility criteria before randomization. The investigator will maintain a screening log to record details of all participants screened and to confirm eligibility or record reasons for screening failure, as applicable.
- Procedures conducted as part of the participant's routine clinical management (eg, blood count) and obtained before signing of informed consent may be utilized for screening or baseline purposes provided the procedure meets the protocol-defined criteria and has been performed within the timeframe defined in the Schedule of Activities.

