10.3.1.2 Secondary Endpoint

The secondary efficacy endpoints are:

- Proportion of participants exhibiting a vIGA-AD score of 0 (cleared) or 1 (almost cleared) AND a ≥ 2 point reduction from Baseline at Week 16;
- Proportions of participants exhibiting a $\geq 50\%$ (EASI-50) reduction from baseline in EASI score at Week 16
- Proportion of participants exhibiting a ≥ 4 point improvement from baseline in Pruritus NRS at Week 16.
- Mean percentage change from baseline in Pruritus NRS at Week 16
- Mean change from baseline in percentage of affected BSA at Week 16

For categorical (proportion) endpoints, the estimate and its corresponding 95% CI of each treatment group will be estimated using Clopper-Pearson method. The difference of the proportion between active treatments and the placebo will be estimated and their corresponding 95% CI will be calculated.

All participants discontinuing prematurely prior to Week 16, regardless of reason, will be counted as non-responders at subsequent visits.

For continuous (percent change from baseline and change from baseline) endpoints, the similar mixed effect model (as used in [Section 10.3.1.1](#)) will be fit with treatment, visit, and treatment-by visit interaction as the fixed effects and measurements within each participant as the repeated measurements. The baseline value will be added into the model as a covariate if necessary, for change from baseline endpoints. Adjusted mean % change (LSMEAN) and unadjusted mean % change with corresponding 95% CI per treatment group will be provided. The difference in adjusted means and corresponding 95% CIs will be provided for the difference between active treatment groups and placebo group at specific visits (eg, week 16 for secondary endpoints).

For participants requiring topical rescue therapy after the first 4 weeks of treatment or for more than 7 days, efficacy assessment after administration of rescue therapy will be considered as missing for continuous endpoints and considered as non-responder for categorical endpoints.

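### The mandatory stop in Section 8.1 for three or more consecutive missed days is not reconciled with the AE restart rule in Section 7.4 or the digoxin hold in Table 7.7.1-1

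*Combined protocol and SAP*

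**What the plan says.** Section 8.1 opens its list with "Participants MUST discontinue investigational product (and non-investigational product at the discretion of the investigator) for any of the following reasons". One item reads "Missed dose of ≥ 3 consecutive days or overall compliance < 85" percent, the latter over more than 30 days counted from Day 1. *Missed dose* is not defined, and no exception is attached to this item.

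Section 7.4, on dosage modification, says: "If a participant interrupts treatment due to an AE, study treatment can be restarted in consultation with the Medical Monitor". It sets no maximum length for the interruption.

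Table 7.7.1-1 prohibits sensitive CYP2C8 or P-gp substrates but adds a qualifier: "digoxin allowed under limited/urgent circumstances; see below". The digoxin row limits it to acute use and tells the site to "stop treatment with IP during treatment with digoxin and for 3 days afterwards". The hold has a fixed end, which implies that study drug then resumes, but the row does not say so.

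None of the three places refers to another.

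For the analysis, Section 10.3.1.2 states for the categorical endpoints: "All participants discontinuing prematurely prior to Week 16, regardless of reason, will be counted as non-responders at subsequent visits". Sections 7.7.2 and 8.1.1 keep participants who stop study drug in the study for their remaining visits and assessments.

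**The concern.** A participant who holds a once-daily drug for three or more days, for an AE or under the digoxin instruction, falls under two provisions. One makes stopping mandatory. The other permits restart or implies it. The site and the Medical Monitor have no text that says which prevails.

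The choice decides who stays on assigned treatment to Week 16. It may also decide who is scored as a non-responder on vIGA-AD response, EASI-50 and the 4-point pruritus response. With about 30 participants per arm, a few such classifications are visible in an arm's rate, so the rule should be fixed before they arise.

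**Working it through.** **Inputs**
- Stopping threshold: 3 or more consecutive days missed, or compliance below 85% over more than 30 days (Section 8.1).
- AE interruption: restart allowed, no length limit (Section 7.4).
- Digoxin hold: days on digoxin plus 3 (Table 7.7.1-1).
- Dosing: once daily for 16 weeks, or 112 days (Section 5.1.2), so each held day is one missed dose.
- Arm size: about 150 randomized equally to 5 groups, 150/5 = 30 (Sections 5.2 and 10.1).

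**The plan's own figure.** Section 10.1 gives 84% power at 30 per group and 78% at 25 (difference 30, SD 43, one-sided 0.05). A two-sample t calculation has noncentrality 30/(43 × √(2/30)) = 2.70 and power 84.7%. At 25 per group the power is 78.4%. The stated figures reproduce, and this point does not dispute them.

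**AE interruptions**

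| Length of hold | Section 7.4 | Section 8.1, read literally |
|---|---|---|
| 1 to 2 days | may restart | not triggered |
| 3 days or more | may restart | must discontinue |

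The conflict is confined to the second row.

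**Digoxin hold.** For k days of digoxin the hold is k + 3 days: 4 days for k = 1 and 10 days for k = 7. If that day's study dose was taken before the first digoxin dose, one fewer dose is missed, so the minimum is (1 − 1) + 3 = 3. The three days afterwards alone reach the threshold, so every hold carried out as directed triggers it.

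**Which half of the Section 8.1 item is responsible.** A 4-day hold leaves compliance at 27/31 = 87.1% on Day 31 and 108/112 = 96.4% on Day 112, both above 85%. Falling below 85% takes 5 missed days by Day 31 (26/31 = 83.9%) or 17 by Day 112 (95/112 = 84.8%). For short holds, the consecutive-day criterion alone creates the conflict.

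**How far it reaches.** Section 8.1 separately requires stopping for Grade 2 or higher cardiac or bone marrow events (ALC excepted) and for Grade 3 events in other systems. Restart after an AE is therefore in question mainly for events below those grades. Digoxin use should be rare. It is excluded at baseline, and Section 6.2 excludes any history of atrial fibrillation or flutter. A new event leading to digoxin may itself require stopping, which is an inference.

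**Size.** One participant who would have responded but is scored as a non-responder lowers the arm's rate by 1/30 = 3.3 percentage points. A participant who would not have responded changes nothing.

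**The case against.** The best defence is that *missed dose* shares an item with percentage compliance and so describes non-adherence, while Section 7.4 uses a different word, interruption, and gives it a specific rule. On that reading there is no conflict. It is plausible and may be what was intended. However, Section 8.1 does not say it, and the same list does write out exceptions elsewhere, for imprisonment and for ALC. Nor can stopping be read as a temporary hold: Sections 9.2.3 and 9.2.6 treat interruption and discontinuation as different things.

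It is also fair that the reach is narrow, that resumption after digoxin is only implied, and that Medical Monitor consultation limits inconsistency. These points reduce the size but do not remove the conflict.

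Several stronger readings are tempting, but the documents do not support them:
- **That the waiver ban settles it.** Section 9 says "Protocol waivers or exemptions are not allowed", but a restart under Section 7.4 applies a protocol provision and is not a waiver. The next item in Section 9 sends immediate safety concerns to the Sponsor to decide on continuing treatment.
- **That sites will certainly diverge.** Restart requires Medical Monitor consultation, so divergence is only a risk.
- **That the rule works against the active arms.** Phase 1 AE data are mixed. AE frequency was similar to placebo in IM018001. In IM018003, AEs occurred in 91.7% on BMS-986166 and 75.0% on placebo, but 1 of 24 and 1 of 8 respectively stopped for AEs. In Part B of the branebrutinib first-in-human study, AEs occurred in 70.8% on active drug and 87.5% on placebo.
- **That a short gap barely changes exposure, so the rule is too strict.** That is a clinical judgement outside this review. It would also rest on the 276 to 321 hour half-life of BMS-986166 and ignore branebrutinib, whose half-life is under 2 hours.

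**Conclusion.** The conflict stands as a matter of text. It applies to AE interruptions of three or more days, mainly for events below the grades that already require stopping, and to every digoxin hold. AE interruptions carry most of the practical weight.

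The effect on the secondary categorical endpoints is at most 3.3 percentage points per affected participant who would otherwise have responded. This assumes 30 per arm and that *discontinuing* in Section 10.3.1.2 includes stopping treatment while remaining in the study, which that section does not specify. A reader might multiply by a guessed number of cases per arm, but the documents give no count, so no total shift or loss of power can be derived.

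An effect on the primary endpoint is not shown. Week 16 EASI is still scheduled after treatment stops, although Section 10.3.1.1 does not say how values after such a stop are used. The point is modest in size but worth correcting, because it governs who stays on treatment and costs little to resolve.

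**What to change.** Reconcile Section 8.1, Section 7.4 and the digoxin row of Table 7.7.1-1 so that all three state one rule on whether AE-driven and protocol-directed interruptions count as missed doses. The digoxin row should say explicitly what happens when the hold ends. The sponsor decides the clinical rule, and this review takes no position on it.

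Record on the eCRF the reason for each interruption of three or more days (non-adherence, AE or protocol-directed hold), so that these participants can be identified in the analysis.

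The cost is about one clarifying sentence in each of three places and one eCRF reason code. No visits or participants are added.

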Nonclinical studies have shown that BMS-986166 has a reduced risk for cardiovascular effects, macular edema, and pulmonary toxicity, compared with other members of the class.

Clinical safety of BMS-986166 was summarized in [Section 3.2.1.5](#).

Based upon nonclinical toxicology findings and the mechanism of action of the compound (immunosuppression), this study incorporates appropriate assessments and risk-mitigation approaches (including careful consideration of appropriate exclusion criteria and monitoring of participants during and after dosing) in combination with conventional safety monitoring. These include assessment for latent tuberculosis (TB) infection (LTBI) and chronic viral infections, and ongoing clinical and laboratory monitoring to reduce the risk from infection, Pulmonary function tests (PFTs), optical coherence tomography (OCT) and close monitoring of vitals and ECGs. Frequent study visits are employed to enhance safety monitoring and reduce risk.

Possible CYP3A4-mediated DDI is anticipated with BMS-986166 as a victim drug when co-administered with CYP3A4 inhibitors or inducers. BMS-986166 did not inhibit any of the human UGTs and CYPs tested and did not induce human CYP1A2, CYP2B6, and CYP3A4. In addition, no inhibition of a panel of human drug transporters was observed for BMS-986166. The inhibition profile, together with the anticipated low efficacious concentration in vivo, suggests low DDI risk as a perpetrator drug.

In vivo studies to evaluate the developmental and reproductive effects of BMS-986166 have demonstrated that, like other SP1R1 modulators, BMS-986166 is a selective developmental toxicant in rats and rabbits, causing cardiac malformations at the lowest doses tested and embryo lethality at higher doses. Therefore, to ensure safety, the investigator will counsel WOCBP to use highly effective contraception, and pregnant women will not be enrolled in this study. It is not known whether BMS-986166 passes into human milk. Therefore, breastfeeding women will not be enrolled in this study.

The accumulated toxicology data and preclinical profile, as well as the Phase 1 clinical data for BMS-986166 suggest that the risks of S1PR1 class-related AEs such as pulmonary and macular edema have been largely mitigated, and the cardiovascular liabilities have been reduced, while

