5.5 Justification for Dose

5.5.1 BMS-986166

The BMS-986166 doses to be evaluated in this study (0.25 mg, 0.5 mg, and 0.75 mg) are based on their safety, tolerability, PK, and PD findings from FIH studies, as well as on nonclinical evaluations as detailed in Section 3.2.1.

The model predictions for participants receiving the 0.5 mg dose of BMS-986166, with average exposures, will typically exhibit reduction in nadir ALC greater than 75% of baseline ALC values and a 2-beat/minute net decrease in HR versus placebo. Translation of exposure-response analyses using ALC, and its relationship to efficacy in preclinical models lends confidence to the efficacy hypothesis at similar exposures yielding similar PD effects in humans.

Safety – In study IM018003, multiple oral doses of BMS-986166 up to 1.5 mg QD for 28 days were safe and generally well tolerated in healthy participants. The most frequently occurring AEs during BMS-986166 administration were lymphopenia (N=15; 62.5%) which is consistent with the pharmacology of the drug; contact dermatitis (N=8; 33.3%), associated with ECG electrode contact sites and increased blood creatine phosphokinase (N=7; 29.2%), assessed by the investigator as unrelated to study drug, were of equal frequency in the placebo and BMS-986166 cohorts; and headache (N=5; 20.8%). Safety results were similarly low and reversible between the 0.25 and 0.75 mg PO QD groups. The no-observed-adverse-effect level (NOAEL) in pivotal nonclinical toxicity studies yield adequate safety margins relative to the projected steady-state exposures at 0.75 mg PO QD.

PK – In the multiple ascending dose (MAD) study IM018003, healthy participants received BMS-986166 solution formulation at dose levels of 0.25, 0.75, and 1.5 mg PO QD for 28 days. Increases in whole blood maximum observed concentration (C_{max}) and area under the concentration-time curve (AUC) over the dosing interval (AUC[TAU]) were approximately dose proportional within the dose levels tested. The mean half-life (T-HALF) at Day 28 ranged from 276 to 321 hours across the dose range tested, indicating that BMS-986166 was slowly eliminated from the body. Consequently, as expected, accumulation after 28 days of dosing (near steady-state) was approximately 14-fold.

[figure not shown]

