6.2 Exclusion Criteria

1) Medical Conditions

- a) Any major illness/condition or evidence of an unstable clinical condition (eg, cardiac, renal, hepatic, hematologic, gastrointestinal, endocrine, pulmonary, neurologic, immunologic, psychiatric) or local active infection/infectious illness that, in the investigator's judgment, will substantially increase the risk to the participant if he or she participates in the study or interfere with the interpretation of study results.
- b) Pregnancy, lactation, or plans for either during the study or the post-study prohibition period (see [Inclusion Criteria](#) for prohibition period duration).
- c) Clinically relevant cardiovascular conditions, including history or presence of:
 - i) Recent (within the last 6 months) occurrence of myocardial infarction, unstable angina, stroke, transient ischemic attack, decompensated heart failure requiring hospitalization, sick sinus syndrome, Class III/IV heart failure ([Appendix 6](#))
 - ii) Prolonged QTcF interval (QTcF > 450 msec males, > 470 msec females), or at additional risk for QT prolongation (eg, hypokalemia, hypomagnesemia, congenital long-QT syndrome)
 - iii) Any prior history of atrial fibrillation or flutter
 - iv) Treatment with Class Ia or Class III anti-arrhythmic drugs or treatment with 2 or more agents in combination known to prolong PR interval
 - v) Patients with other pre-existing stable cardiac conditions who have not been cleared for the study by an appropriate cardiac evaluation by a cardiologist
- d) Clinically relevant pulmonary conditions, including:
 - i) Unstable asthma or chronic obstructive pulmonary disease (COPD) (eg, acute episodes of exacerbation [nocturnal episodes, sudden episodes triggered by unidentifiable factors] despite a stable regimen of relevant medications); prior episode(s) of life-threatening asthma or COPD; or asthma or COPD that requires systemic glucocorticoid or biologic treatment, or inhaled budesonide or equivalent at > 1200 µg/day or fluticasone propionate at > 880 µg/day along with another anti-asthma/COPD drug such as a long-acting beta-agonist.
 - ii) Severe untreated sleep apnea
 - iii) Forced expiratory volume (FEV1) or forced vital capacity (FVC) < 70% of predicted values at screening

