7.3 Blinding

This is a randomized double-blinded study. Access to treatment codes will be restricted from all participants, and site and BMS personnel prior to database lock, with exceptions as specified below.

Blinding of treatment assignment is critical to the integrity of this clinical study. However, in the event of a medical emergency or pregnancy in an individual participant in which knowledge of the investigational product is critical to the participant's management, the blind for that participant may be broken by the investigator. The participant’s safety takes priority over any other considerations in determining if a treatment assignment should be unblinded.

Before breaking the blind of an individual participant's treatment, the investigator should determine that the unblinded information is necessary, ie, that it will alter the participant's immediate management. In many cases, particularly when the emergency is clearly not related to the investigational product, the problem may be properly managed by assuming that the participant is receiving active product. It is highly desirable that the decision to unblind treatment assignment be discussed with the Medical Monitor, but the investigator always has ultimate authority for the decision to unblind. The actual task of unblinding can be delegated by the investigator to a designee assigned the task on the Delegation of Authority. The Principal Investigator or appointed designee should only call in for emergency unblinding AFTER the decision to unblind the participant has been documented.

For this study, the method of unblinding for emergency purposes is through the IRT system. In case of an emergency, the investigator has unrestricted access to randomization information via IRT and can break the blind through the IRT system without prior approval from the Sponsor.

After the unblinding, the investigator shall notify the Medical Monitor and/or Study Director. The method of unblinding for emergency purposes is described in the IRT Manual. Participant and

unblinded treatment information and the reason for the blind being broken must be recorded on the appropriate study status page of the electronic case report form (eCRF).

In cases of accidental unblinding, contact the Medical Monitor and ensure every attempt is made to preserve the blind.

Any request to unblind a participant for non-emergency purposes should be discussed with the Medical Monitor.

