Refer to the [Schedule of Activities](#) for data to be collected at the time of treatment discontinuation and follow-up and for any further evaluations that can be completed

In the case of pregnancy, the investigator must immediately, within 24 hours of awareness of the pregnancy, notify the BMS Medical Monitor/designee of this event. In most cases, the study treatment will be permanently discontinued in an appropriate manner (eg, dose tapering if necessary for participant safety). Refer to [Section 9.2.5](#) Pregnancy.

All participants who discontinue study treatment should comply with protocol specified follow-up procedures as outlined in [Section 2](#). The only exception to this requirement is when a participant withdraws consent for all study procedures including post-treatment study follow-up or loses the ability to consent freely (ie, is imprisoned or involuntarily incarcerated for the treatment of either a psychiatric or physical illness).

If study treatment is discontinued prior to the participant's completion of the study, the reason for the discontinuation must be documented in the participant's medical records and entered on the appropriate case report form (eCRF) page.

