9.2.5 Pregnancy

If, following initiation of the study treatment, it is subsequently discovered that a participant is pregnant or may have been pregnant at the time of study exposure, including during at least for 3 months after study product administration, the investigator must immediately notify the BMS Medical Monitor/designee of this event and complete and forward a Pregnancy Surveillance Form to BMS Designee within 24 hours of awareness of the event and in accordance with SAE reporting procedures described in [Appendix 3](#).

If the investigator determines a possible favorable benefit/risk ratio that warrants continuation of study treatment, or re-initiation of study treatment, a discussion between the investigator and the BMS Medical Monitor/designee must occur.

Follow-up information regarding the course of the pregnancy, including perinatal and neonatal outcome and, where applicable, offspring information must be reported on the Pregnancy Surveillance Form.

Any pregnancy that occurs in a female partner of a male study participant should be reported to Sponsor or designee. In order for Sponsor or designee to collect any pregnancy surveillance information from the female partner, the female partner must sign an informed consent form for disclosure of this information. Information on this pregnancy will be collected on the Pregnancy Surveillance Form.

If any sexual activity (eg, vaginal, anal, oral) has occurred between a male participant and a pregnant partner(s) without the use of a condom during and at least for 3 months, after study product administration, the information should be reported to the Sponsor or designee, even if the male participant has undergone a successful vasectomy.

In order for Sponsor or designee to collect any pregnancy surveillance information from the female partner, the female partner(s) must sign an informed consent form for disclosure of this information. Information on the pregnancy will be collected on the Pregnancy Surveillance Form.

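### Pregnancy is not a mandatory reason to stop study drug, and Section 9.2.5 contemplates continuing or restarting it

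*Combined protocol and SAP*

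**What the plan says.** Section 8.1 opens its list with "Participants MUST discontinue investigational product (and non-investigational product at the discretion of the investigator) for any of the following reasons". Fourteen bullets follow, including a live vaccine, three consecutive days of missed doses and several laboratory thresholds. None names pregnancy.

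Pregnancy has its own paragraph further down in Section 8.1. The investigator must notify the Medical Monitor within 24 hours, and then: "In most cases, the study treatment will be permanently discontinued in an appropriate manner (eg, dose tapering if necessary for participant safety". The paragraph refers to Section 9.2.5, which contains a clause beginning "If the investigator determines a possible favorable benefit/risk ratio that warrants continuation of study treatment, or re-initiation of study treatment" and ending with a required discussion between the investigator and the Medical Monitor.

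Section 7.4 states "Dose reductions or dose escalations are not permitted", for all arms. Section 7.3 says that in a medical emergency or pregnancy where knowing the treatment is critical to management, "the blind for that participant may be broken by the investigator". On risk, Section 3.3.1 says that "BMS-986166 is a selective developmental toxicant in rats and rabbits, causing cardiac malformations at the lowest doses tested", with embryo lethality at higher doses.

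**The concern.** A positive test during treatment leaves a decision open that the protocol's own risk section appears to have settled. The exception to stopping has no stated criteria. It does not require agreement from the Medical Monitor, knowledge of the participant's arm, or evidence that the test was false. An investigator could therefore keep a pregnant participant on blinded drug after one conversation.

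The stake is avoidable fetal exposure to a compound with malformation findings in two species, set against a benefit that this trial is the first to test in this disease. The precautions elsewhere make the gap stand out. Section 6.1 requires male participants to use condoms even when the partner is already pregnant, and Section 9.2.5 asks for reports of unprotected contact with a pregnant partner. The protocol thus guards against exposure through semen but leaves open direct daily dosing of a pregnant participant.

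**Working it through.** The plan gives no figure to reproduce. The main check is of text, followed by arithmetic on how often the rule would be used.

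**Is there a mandatory stop anywhere?**

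1. Section 8.1 list: pregnancy is absent from all 14 bullets. The nearest bullet covers an adverse event, laboratory abnormality or intercurrent illness, but it depends on the investigator's opinion.
2. Section 8.1 pregnancy paragraph: permanent discontinuation is the default, but only for most cases. The remaining cases are not described.
3. Section 9.2.5: this supplies the remaining cases. The trigger is the investigator's view that benefit/risk may be favourable; the only requirement is a discussion.
4. Section 7.3: unblinding is permitted, not required, and neither pregnancy paragraph makes it a condition of continuing.
5. Schedule of Activities, Sections 6.1, 6.2 and 9.2, and Appendices 3 and 4: these prevent, detect, exclude at entry or report pregnancy. None requires a stop.

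With 1:1:1:1:1 allocation, a blinded decision concerns BMS-986166 with probability 3/5, branebrutinib 1/5 and placebo 1/5.

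**How often would it arise?**

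Expected on-treatment pregnancies = W × f × 112/365, where W is the number of women of childbearing potential and f is the annual contraceptive failure rate. W is not in the protocol; I assume 30 to 60. For f I assume 1%, the ceiling in the Section 6.1 definition of a highly effective method. The 112 days are 16 weeks of treatment.

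| W | Expected, all arms | On BMS-986166 (× 3/5) |
|---|---|---|
| 30 | 30 × 0.01 × 112/365 = 0.09 | 0.06 |
| 60 | 60 × 0.01 × 112/365 = 0.18 | 0.11 |
| 150 (every participant; not realistic, since men are enrolled) | 150 × 0.01 × 112/365 = 0.46 | 0.28 |

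These count pregnancies. Continued dosing also needs a decision against the default, whose probability is unknown.

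**Pharmacokinetic context**

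Section 5.5.1: "The mean half-life (T-HALF) at Day 28 ranged from 276 to 321 hours across the dose range tested". In days, 276/24 = 11.5 and 321/24 = 13.4. Five half-lives after an immediate stop are 5 × 11.5 = 57.5 days to 5 × 13.375 = 66.9 days. This is for BMS-986166; no human half-life is given for its active phosphate. The washout is the same under the present text and under the fix. What the fix removes is any dose taken after the positive test.

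**Would a short hold be workable?**

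Section 8.1 also requires discontinuation after three or more consecutive missed days, or compliance below 85% over more than 30 days from Day 1. Over 31 days the allowance is 0.15 × 31 = 4.65 days, so five held days (26/31 = 83.9%) breach it. A restart after a false positive therefore needs an explicit exemption.

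**The case against.** The strongest reply is that the safe course is already the stated default. Section 8.1 has a pregnancy paragraph with 24-hour notification and permanent discontinuation as the norm. Section 9.2.5 requires a discussion without saying in terms that treatment may go on. It also covers a participant who may have been pregnant at exposure, not only a confirmed ongoing pregnancy. The three-day missed-dose rule, read alone, bars many restarts, although Section 7.4 allows restart after an interruption for an adverse event. Prevention is strong: highly effective contraception, testing at every visit and exclusion at entry. All of this stands, and it keeps the point minor. It does not close the gap, because the exception is written in and has no criteria.

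A reader might also infer several stronger things that the documents do not support:

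- **A contradiction with exclusion criterion 1b.** That criterion, "Pregnancy, lactation, or plans for either during the study or the post-study prohibition period", governs entry and is not an on-treatment stopping rule.
- **A planned taper against Section 7.4.** The taper is a conditional example, and nothing in the protocol says either drug needs tapering. The wording does not fit Section 7.4 but has no identified trigger.
- **Equal concern for every active arm.** The malformation finding is for BMS-986166. For branebrutinib, Section 3.3.2 reports developmental toxicity in rabbits at 53 times the exposure of the 9 mg dose, together with maternal toxicity, and none in rats up to 437 times human exposure.
- **A measure of fetal risk from the washout time.** Section 3.3.1 gives no exposure multiple for the malformations, so no conversion is possible.

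**Conclusion.** The point holds as a minor, low-frequency matter of participant safety. Pregnancy is not a mandatory stop, the default has an open exception, and Section 9.2.5 contemplates continuing or restarting without approval, unblinding or a confirmed negative test. That is out of line with the animal findings for the drug in three of the five arms and with the unproven benefit in this disease.

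The expected number of on-treatment pregnancies is well below one: 0.09 to 0.18 overall and 0.06 to 0.11 on BMS-986166. These figures rest on the assumed number of women and the assumed failure rate. The textual finding rests on neither.

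A reader might infer that the protocol plans to dose through pregnancy, or that the trial's results are at risk. The first goes beyond the text, since stopping is the norm. The second has no basis: neither the primary analysis nor the dose comparison is affected.

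**What to change.** 1. Add *Pregnancy* to the mandatory list in Section 8.1.
2. Replace the sentence on most cases with: *Study drug is stopped on the day of a positive pregnancy test and permanently discontinued once pregnancy is confirmed.* Drop the taper example.
3. Delete the continuation and re-initiation paragraph in Section 9.2.5.

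If restart after a false positive is wanted, the inserted text must carry its own condition; otherwise it would be a broader permission than the paragraph it replaces: *Study drug may be restarted in consultation with the Medical Monitor only if a serum pregnancy test is negative; days held for this reason do not count towards the missed-dose and compliance rules in Section 8.1.*

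The cost is wording at the next amendment and a check that the consent form, which is not among the documents reviewed, says the same. The sponsor gives up investigator discretion to continue in a rare case. The restart option would add an occasional confirmatory serum test, which the on-treatment schedule does not now include. No extra scheduled visits or drug supplies are needed.
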